#### **STATEMENT OF COMPLIANCE FOR NON DRUG OR DEVICE CLINICAL TRIALS**

This document is a protocol for a clinical research study. The study will be conducted in compliance with all stipulations of this protocol, the conditions of ethics committee approval, the NHMRC National Statement on Ethical Conduct in Human Research (2007) and the [Handbook for Good Clinical Research Practice \(GCP\)](#)

## 2. SYNOPSIS

Sensory-based intervention (SBI) aims to improve undesirable behaviours of children with autism spectrum disorder (ASD). Proprioceptive input is one type of SBI that is hypothesised to organise the central nervous system and aid sensory regulation. Proprioceptive input arises as a result of an individual's own movement, specifically, active muscle contraction against resistance. However the research on SBI is inconclusive as it remains unclear how to effectively use proprioceptive input to improve behaviour of children with ASD. This study aims to understand how undesirable behaviours of children with ASD and co-occurring sensory over-responsiveness change following parent-facilitated proprioceptive input. The research uses an ABA single-case design (SCD) research over a 9 week period. Five children, aged 4-14 years, with ASD and co-occurring sensory over-responsiveness will participate in the study. Following training from the researcher (occupational therapist), their parents will facilitate responsive, proprioceptive input during play and tasks in the home environment. The parents will score their target behaviour prior to intervention (A1), during the proprioceptive intervention (B), and following the intervention period (A2) on a visual analogue scale. Visual analysis of the VAS data for each participant will be used to establish preliminary evidence of a causal relationship between parent-facilitated, responsive proprioceptive input and undesirable behaviours for children with ASD and co-occurring sensory over-responsiveness.

## 3. RATIONALE / BACKGROUND

Children with ASD experience difficulties in sensory processing which impact their day to day lives (Howe & Stagg, 2016; Lane, Young, Baker, & Angley, 2010). A relatively recent inclusion in diagnostic criteria acknowledges "hyper- or hypo-reactivity to sensory input or unusual interest in sensory aspects of the environment" as possible contributors to restricted and repetitive behaviours (American Psychiatric Association, 2013). When a child experience hyper-reactivity, they are being over-responsive to an incoming sensory input which results in a strong, often negative response; an undesirable behaviour (Bundy, 2002).

Sensory-based intervention (SBI) is one type of intervention used to target over-responsiveness to sensory input. SBI is characterised by structured, adult-directed sensory strategies that are integrated into the child's daily routine to improve undesirable behaviours (Case-Smith, Weaver, & Fristand, 2015). Two systematic reviews examining research from 2000-2013 (Case-Smith et al., 2015; Watling & Hauer, 2015) propose that there is currently

insufficient evidence for implementing SBI with children with ASD. SBI research varies in how sensory input provided, the frequency and duration of the input and the context which the sensory input is delivered. Studies have used purely proprioceptive input by use of weighted vests (Cox, Gast, Luscre, & Ayres, 2009; Fertel-Daly, Bedell, & Hinojosa, 2001; Hodgetts, Magill-Evans, & Misiaszek, 2011a, 2011b; Leew, Stein, & Gibbard, 2010; Quigley, Peterson, Frieder, & Peterson, 2011; Reichow, Barton, Neely Sewell, Good, & Wolery, 2010); combinations of proprioceptive and tactile input through massage (Escalona, Field, Singer-Strunck, Cullen, & Hartshorn, 2001; Silva, Schalock, Ayres, Bunse, & Budden, 2009) or brushing (Davis, Durand, & Chan, 2011); combinations of proprioceptive and vestibular input using therapy balls (Bagatell, Mirigliani, Patterson, Reyes, & Test, 2010; Schilling & Schwartz, 2004); and combinations of all three forms of input through implementing sensory diets (Bongatt & Hall, 2010; Devlin, Healy, Leader, & Hughes, 2011; Devlin, Leader, & Healy, 2009). There are mixed results within each combination of sensory input provided to children. Likewise, there is not clear what frequency and duration or context results in more efficient improvements in undesirable behaviours for children with ASD.

This study will primarily use proprioceptive input as the form of sensory input provided to children with ASD. This is because proprioception is generally the most organising type of sensation and children are rarely sensitive to proprioceptive input. The primary sensory receptors for proprioceptive input are small parts of muscle. These muscles are activated when a child moves a muscle, specifically, when the muscle moves against resistance. Therefore, activities where a child is actively pushing, pulling, carrying, lifting, chewing, sucking or gaining another form of resistance, are providing proprioceptive input. Proprioceptive input is calming to the child as it provides an inhibitory effect on the central nervous system (Bundy, 2002). Although the input may be gained by different parts of the body, such as arms, legs or mouth, the input travels directly to the brain to provide a generalised calming effect on the child's whole body.

SBI is characterised by sensory strategies that are integrated into the child's daily routine. However, the frequency of SBI in the above studies is not responsive to the unpredictability of a child's daily routine. The majority of SBI studies used pre-determined times for the sensory strategy, rather than being proactive to the child's needs. As SBI is designed to support a child's regulation, it is recommended that they the intervention be implemented as a response to the child's arousal, such as, when they experience over-responsiveness (Case-Smith et al., 2015). Therefore, the proposed study adopts a responsive SBI. Sensory input was generally applied for 10-15 minutes, this duration will be replicated in the current study.

SBI is characterised by adult-directed activities, and despite being arguably the most influential adult in a child's life, parents are featured in a minority of the studies. The majority of studies mentioned above are set in the school, or preschool, environment and rely on interventions being implemented by teachers and teachers' aids. To replicate real-world occupational therapy and enrich family-centeredness, parents will facilitate the SBI in the home environment in the proposed study.

It is clear that children with ASD exhibit behaviours related to over-responsiveness, although it is currently unclear on how to best support them. We know that proprioceptive input has a general calming effect on the body. However, SBI drawing on proprioception has mixed outcomes with the studies drawing upon unconvincing strategies to provide the input; such

as frequency of the input and context where the input is provided. There is an upmost need for further research in how to provide successful proprioceptive input to improve undesirable behaviours of children with ASD and co-occurring sensory over-responsiveness.

#### 4. AIMS / OBJECTIVES / HYPOTHESES

**Research Question:** How do undesirable behaviours of children with ASD and co-occurring sensory-over responsiveness change following parent-facilitated proprioceptive input?

#### 5. PARTICIPATING SITES

The research will be conducted in the home environments of participants in South Eastern Sydney.

#### 6. RESEARCH PLAN / STUDY DESIGN

**Type of study:** This study is a prospective study.

**Study Design:** This research will adopt a quantitative approach, using a single case design (SCD). SCD was chosen over the 'gold standard' of quantitative research, randomised controlled trial (RCT), for a number of reasons. First, SCDs require fewer participants to obtain reputable results. Second, SCD eliminates the need for control groups and thus removal of the ethical dilemma of withholding treatment to a group of children. Third, SCD allows for individualised intervention matched to the family's priorities and needs. Finally, SCD is a less intrusive research design allowing families to continue their regular routine with minimal adjustments (Bulkeley, Bundy, Roberts, & Einfeld, 2013; Mesibov & Shea, 2011; Perdices & Tate, 2009). SCD research establishes the child as his/her own control. The child's target undesirable behaviour is rated with and without intervention, that is, the implementation of parent-facilitated, responsive proprioceptive input. Changes in target behaviour are measured by analysing the behaviour prior to the intervention, during the intervention, and when the intervention is withdrawn (Kazdin, 2011). SCD research can provide a causal relationship between proprioceptive input and undesirable behaviours for children with ASD. However, the ABA design does not allow for three intervention effects to be analysed which Kratochwill et al. (2013) recommends for causation to be established. Instead, the ABA design will allow for identification of preliminary evidence of the casual relationship as proposed by Johnston and Pennypacker (2009).

[figure not shown]
**Population / Sample Size:** This study includes both children and their parents as participants. The study will use parent-report for the children's age and diagnosis. Children are required to be aged 3-14 years of age and have a diagnosis of ASD. Children with co-morbidities (for example, physical disabilities, moderate-profound cognitive impairments, severe mental health disorders) *will not* be eligible for the study. However, ASD is commonly paired with a mild cognitive impairment and/or mental health conditions. Therefore, children with a diagnosis of mild global developmental delay (GDD), mild intellectual disability (ID), mild anxiety and/or ADHD *will* be eligible for the study. Parents and children will be required to reside in South Eastern Sydney. Due to practical reasons, parents will be required to speak fluent English. To increase validity of the results, participants can be receiving other

services but need to agree that the target undesirable behaviour of the study will not be addressed by other therapies during the study period.

Due to SCD using the child as their own control, they yield robust findings with a small number of participants (Bulkeley et al., 2013). Furthermore, standards for SCD research recommend at least three replications, or three participants, are required to establish a causal relationship between proprioceptive input and improving undesirable behaviour for children with ASD (Kratochwill et al., 2013). Therefore, five families will be recruited for the study.

**Procedure and measures:** The procedure for this research has been based on the recent work by Bulkeley, Bundy, Roberts, and Einfeld (2016). Similarly to Bulkeley et al. (2016), an A-B-A SCD will be used over a 9 week period (see figure 1). The A-B-A design will allow for an initial baseline measurement (A1), the intervention period (B) and a return-to-baseline phase (A2). Following screening of a sensory over-responsiveness, the initial baseline (A1) will occur for 2 weeks, whereby the parent will rate their child's target undesirable behaviour at the conclusion of each day. Next, during the 5-week intervention phase (B), the researcher, who is an experienced and practicing occupational therapist, will visit 5 times to individually provide the participants with education, programming, modelling and follow up. During the 'B' phase the parent will continue to rate the target behaviour daily. Lastly, the return-to-baseline (A2) will involve the parent ceasing proprioceptive activities (intervention) and continuing to score the target behaviour daily. The A-B-A design allows for the functional link between behaviour change and the intervention to be measured (Bulkeley et al., 2013; Kazdin, 2011).

Figure 1: Research Procedure

Prior to beginning the research phase (A-B-A), screening will take place to: 1) ensure the children in the study have sensory over-responsiveness (defined by sensory avoiding and/or

sensitivity behaviours as identified by Sensory Profile 2 Child; SP-2) and 2) to identify a target undesirable behaviour for each child. Screening will involve the researcher completing the SP-2 with each parent. Please see appendix A for copy of SP-2. This assessment is a questionnaire for age 3:0 to 14:11 years in which the caregiver marks how frequently the child engages in behaviours listed on the form. The SP-2 has demonstrated good validity and reliability (internal consistency, test-retest reliability and interrater reliability); with these psychometric properties inclusive of children with ASD (Dunn, 2014b). The norm-referenced results rate the child's responses (low registration, seeking, sensitivity, avoiding) in a range of sensory areas: auditory, visual, touch, movement, body position and oral sensory (Dunn, 2014a). If results from the SP-2 show the child as having "much more than others" response for avoiding and or sensitivity, meaning the child displays over-responsiveness, the child will be eligible for the study.

The researcher and parent will identify a target undesirable behaviour (that is a result of sensory over-responsiveness) from a sensory domain of SP-2 where the child responded 'much more than others'. For example, if the child scores 'much more than others' in the area of touch, the researcher will refer to the 'almost always' and 'frequently' answers for the questions asked about touch. This will show what behaviours, related to sensory touch, are impacting the most on the the child and their family's day to day lives. Using the touch example, a target behaviour deduced from the SP-2 may be 'shows an emotional or aggressive response to being touched'. The impact (e.g. level of aggression from touch) of the target behaviour will be rated by the parent daily during the research period.

SCD research requires ongoing monitoring to effectively track individual outcomes (Mesibov & Shea, 2011). A Visual Analogue Scale (VAS) will be used to track the child's behaviour throughout the research period. Please see appendix B for copy for VAS. The VAS is the chosen instrument because it is individualised, user friendly, inexpensive and has good reliability and construct validity (Chafouleas, Sanetti, Kilgus, & Maggin, 2012; Wewers & Lowe, 1990). The VAS will be individualised for each participant, for example, using the behaviour defined above, the VAS would record parent daily perceptions from 'no aggression to 'high aggression'. To ensure consistency in the recognition of the target behaviour, the same parent will score the behaviour throughout the research period and a clear description of the behaviour will be provided on each VAS. Each night, parents will be required to 1) indicate whether the child presents the undesirable behaviour that day, and 2) mark on a line how they perceived the impact of the target behaviour that day. To make rating accessible and efficient, parents will use the application P.I.E.L. Survey (Jessup, Bian, Chen, & Bundy, 2012) where they will be able to access their individualised VAS each day. The parents will be able to loan an iPod touch from The University of Sydney if they do not have own a compatible iOS device. Using P.I.E.L. Survey allows the researchers to download all the participant's responses. By utilising a VAS, a parent-rated assessment measure, the effects of the researcher also being the interventionalist are minimised.

The design of this SCD research study mimics real life therapy strategies whereby parents implement intervention throughout the day with their child. However, to analyse a causal relationship between the intervention and the undesirable behaviours, evaluation at the end of each day which encompasses the parent's perceptions of their child's behaviour throughout the day is included.

**Intervention:** In line SCD research, the intervention has been developed to reflect real world occupational therapy with an aim of being easily embedded into regular routines, with minimal additional demands for participants. Furthermore, each participant is able to work towards an outcome meaningful to them. Each child has their own target behaviour which is measured using the VAS and their own set of proprioceptive activities that work for their family. However, important to the research design is the consistency of proprioceptive input being received by the child in the set activities (Mesibov, 2011). Therefore, to ensure each child is correctly receiving proprioceptive input, the intervention phase includes: education, programming, modelling and follow up.

Education will involve the researcher (occupational therapist) explaining the fundamentals of sensory over-responsiveness to parents and how to be responsive through understanding the signs of over-responsiveness and triggers for the child's target behaviour. The researcher will work with the parent to develop a program of activities that primarily provide proprioceptive input to the body. These activities will be those that can easily be implemented in the home environment and in the child's established routine, typically embedded within play or jobs around the house. The recommended activities do not involve expensive equipment or specialised training to administer. The parent will facilitate the proprioceptive activities when triggers of the target behaviour are present or when they observe the child showing signs of over-responsiveness. Please see appendix C for parent handout. The researcher will model how to engage the child in these activities and how to perform the activities correctly in order to provide proprioceptive input. The parent will facilitate the activities for 10-15 minutes, or until they see a positive change in the child's face and body language. This time frame was chosen as it is a commonly used time frame for implementing sensory based intervention (e.g. Bagatell et al., 2010; Escalona et al., 2001; Reichow et al., 2010; Schilling & Schwartz, 2004; Silva et al., 2009). The researcher will visit the home weekly during the intervention 'B' phase, ideally when the target behaviour is expected to occur, to follow up and provide further guidance to the parents.

Due to the target behaviour being a behaviour scored as 'always' or 'frequently' on the SP-2, it is anticipated the behaviour will occur almost, if not, daily and may even occur numerous times a day. It is not anticipated that the intervention will remove the behaviour altogether, but rather, from being responsive to the child's signs of entering high arousal and becoming over-responsive to certain sensory stimuli, the perceived impact of undesirable behaviour will be minimised.

**Expected duration of study:** The research period for each participant is 9 weeks. The total length of the study will be from July 2017 to July 2018.

**Data analysis:** Data analysis will involve visual analysis of the VAS results for each participant. As with SCD research, each child is his/her own control, and therefore, each child's data will be analysed individually. The visual analysis will aim to find a causal relationship between the intervention and the child's undesirable behaviour, and the strength of this relationships, then generate a hypothesis about the relationship (Kazdin, 2011; Kratochwill et al., 2013)

The first step in the visual analysis will be establishing a projected level of baseline (A1) data, that is, determining whether the target undesirable behaviour is steady, increasing, decreasing or adopting another pattern over the 2 weeks prior to intervention. Next, the data

within each child's B and A2 phase will be examined to establish the within-phase patterns. The data from each phase will then be compared visually to the data in the adjacent phase (A1 to B and B to A2). This will be done for each child and will determine if the addition of the proprioceptive intervention has an effect on undesirable behaviour. The final step will include integrating the information from each phase (A1, B and A2) to establish preliminary evidence of a causal relationship (Kratochwill et al., 2013).

Throughout the analysis phase, six outcome-measure features will be used to examine the within- and between-phase data patterns (Kratochwill et al., 2013): level (mean of the data points); trend (best-fitting straight line); variability (scatter of points); immediacy of the effect (immediate change in level of data points in adjacent phases); overlap (same data level in adjacent phases) and; consistency of data patterns across similar phases (similarity of data level, trend and variability in A1 and A2). Analysis of these six outcome measures across and within the phases, will support the argument for preliminary evidence of a causal relationship between parent-facilitated, responsive proprioceptive input and undesirable behaviours for children with ASD and co-occurring sensory over-responsiveness.

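### Five families are justified by between-child replication that establishes causality, but the design section allows only preliminary evidence and the analysis never counts effects across children

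*Protocol*

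**What the plan says.** All of the relevant text is in section 6 of the Protocol.

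- **Population / Sample Size.** The rationale is that "standards for SCD research recommend at least three replications, or three participants, are required to establish a causal relationship", and it continues: "Therefore, five families will be recruited for the study". No power, precision or dropout calculation is given.
- **Study Design.** Citing the same 2013 standard, this paragraph says that "the ABA design does not allow for three intervention effects to be analysed", and that instead "the ABA design will allow for identification of preliminary evidence of the casual relationship" (sic).
- **Data analysis, aim.** "The visual analysis will aim to find a causal relationship between the intervention and the child's undesirable behaviour, and the strength" of that relationship.
- **Data analysis, steps.** Because each child is its own control, "each child's data will be analysed individually". Each phase is "compared visually to the data in the adjacent phase (A1 to B and B to A2"). Then: "The final step will include integrating the information from each phase (A1, B and A2) to establish preliminary evidence of a causal relationship". The consistency feature is defined as similarity between A1 and A2, not between one child and another.

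The closing sentence of Data analysis, like the Synopsis, states the conclusion for children with ASD and sensory over-responsiveness in general, at the level of preliminary evidence.

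**The concern.** The number five has one quantitative support: it exceeds a minimum of three replications or participants. That support is tied to establishing causality, a level of claim that the design paragraph disowns while citing the same source.

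The more consequential part is that replication protects a conclusion only if someone counts it. If the five children serve as replications of one another, the analysis has to say what a replicated effect is and how many are needed. Without that, the same five graphs could be summarised as supportive whether one child or all five responded. The ratings come from the parent who delivers the intervention and knows the phase, so the study-level reading should not be left until the graphs have been seen.

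**Working it through.** There is no sample-size formula to reproduce. The check is a count, followed by an illustration of what the count controls.

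**1. The Protocol's own figure.** Minimum three participants, planned five: 5 ≥ 3, so the between-child count is met with a margin of two families.

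**2. Within a child.** A-B-A has two phase changes (A1 to B, B to A2): 2 < 3. The design paragraph is right about a single child.

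**3. Across the study.** 5 children × 2 changes = 10 phase contrasts, or five between-child replications. Three effects can therefore be reached only by counting across children.

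**4. Does the analysis count across children?** Taking the steps of Data analysis in order:

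| Step | Level |
|---|---|
| Describe the A1 pattern | within child |
| Describe the B and A2 patterns | within child |
| Compare adjacent phases | within child, repeated for each child |
| Final step: integrate A1, B and A2 | across phases |
| Consistency feature | A1 against A2 |

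No step combines, compares or counts children.

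**5. Illustration of why the count matters.** The inputs from the Protocol are daily ratings over 2, 5 and 2 weeks, that is 14, 35 and 14 points, and five children. The assumptions are mine: no treatment effect, independent children, and lag-1 autocorrelation from 0 to 0.7. The minimal rule is that a child counts if the B mean lies below both A means by any amount. This is not the plan's six-feature visual analysis.

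At zero autocorrelation, with unit variance:
- Var(A1 − B) = 1/14 + 1/35 = 0.100, and the same for A2 − B.
- Cov(A1 − B, A2 − B) = 1/35 = 0.0286.
- Correlation = 0.0286/0.100 = 0.286.
- P(both differences positive) = 1/4 + arcsin(0.286)/(2π) = 0.296.
- P(at least 1 of 5) = 1 − (1 − 0.296)^5 = 0.827.
- P(at least 3 of 5), binomial with p = 0.296: 0.158.

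Simulation (200,000 series per autocorrelation value) adds the other values, and also an example margin that requires both differences to exceed 0.5 of that child's own A1 standard deviation:

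| Child-level rule | Per child | At least 1 of 5 | At least 3 of 5 |
|---|---|---|---|
| B mean lowest, any amount | about 0.30 | 0.82-0.83 | 0.15-0.16 |
| Both differences above 0.5 A1 SD | 0.013-0.107 | 0.06-0.43 | at most about 0.010 |

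The lower-row figures for at least one child follow from 1 − (1 − 0.013)^5 = 0.06 and 1 − (1 − 0.107)^5 = 0.43. The upper ends belong to autocorrelation 0.7. There, the margin alone still leaves a substantial chance of one spurious child, and it takes the count across children to bring the study-level probability down to about 0.01.

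**The case against.** **The passages need not conflict.** One concerns effects within an A-B-A sequence, the other replication between participants. Two per child is too few, five children are enough, and both statements can be true. This stands as a possible reading, but the Protocol does not draw the distinction, and on that reading the analysis needs the cross-child step that it lacks.

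**The claim is already limited.** The Synopsis, the design paragraph, the end of Data analysis and section 9 all speak of preliminary evidence. This stands. A reader might infer that the study plans to declare causality established. The documents do not support that: the sample-size sentence and the stated aim of the visual analysis are out of line with the rest of the text.

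**Counting rules belong in an SAP.** This stands in part. The margin and other detail could be left there. But the Protocol itself rests its sample size on replication and then sets out an ordered analysis whose named final step does not use it. An SAP could add a count, but it would not correct the rationale.

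**The chance figures test another rule.** This stands. A reader might take 0.30 or 0.82 as this plan's error rate, or conclude that chance patterns will be reported as evidence. Neither follows. The plan also looks at trend, variability, immediacy, overlap and consistency, and would probably be stricter. The timeline also puts all families on the same calendar dates, which weakens the independence assumption.

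**One child sufficing is an inference.** The plan does not say that a single child is enough, and it repeats the comparison for every child. What can be said is that nothing in it rules this out.

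**Conclusion.** The point holds at moderate severity. The sample-size rationale claims a level of inference that the design paragraph denies. If it is read instead as between-child replication, the analysis never uses that replication. These two findings rest on the text alone.

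The size of the consequence cannot be fixed from the documents, because the plan does not define an effect in a child. The probabilities are illustrations that depend on the assumed rule, autocorrelation and independence. Within those assumptions, requiring three of five rather than accepting any one lowers the chance result from 0.82-0.83 to 0.15-0.16 under the loosest rule.

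A reader might also infer that five families is the wrong number, or that the cited standard has been misreported. The first does not follow, since five exceeds the stated minimum of three. The second cannot be checked from the documents.

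**What to change.** 1. **Population / Sample Size:** reword the rationale to say that five families provide between-child replication, with a minimum of three, of preliminary evidence, and not established causality.
2. **Data analysis, aim:** replace the aim of finding a causal relationship with that of finding preliminary evidence of one, as the rest of the Protocol does.
3. **Data analysis, new final step, fixed before data are seen:** state what counts as an effect in a child (improvement from A1 to B and reversal from B to A2, judged on the six features). Report all five children whatever their result. Claim study-level preliminary evidence only if at least three of the five show the effect. Three is the Protocol's own replication number. If a numerical margin is wanted, 0.5 of the child's A1 standard deviation is only an example, and the sponsor should choose and justify its own.

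The cost is a few lines of text, with no added participants, visits or data. The downside is a slightly less favourable claim: a result in one or two children would be reported, but would not support a study-level conclusion.
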